# 8 Safety and Adverse Events

## 8.1 Definitions

### Unanticipated Problems Involving Risk to Subjects or Others

Any incident, experience, or outcome that meets all of the following criteria:

- Unexpected in nature, severity, or frequency (i.e. not described in study-related documents such as the IRB-approved protocol or consent form, the investigators brochure, etc)
- Related or possibly related to participation in the research (i.e. possibly related means there is a reasonable possibility that the incident experience, or outcome may have been caused by the procedures involved in the research)
- Suggests that the research places subjects or others at greater risk of harm (including physical, psychological, economic, or social harm).

### Adverse Event

An **adverse event** (AE) is any symptom, sign, illness or experience that develops or worsens in severity during the course of the study. Intercurrent illnesses or injuries should be regarded as adverse events. Abnormal results of diagnostic procedures are considered to be adverse events if the abnormality:

- results in study withdrawal
- is associated with a serious adverse event
- is associated with clinical signs or symptoms
- leads to additional treatment or to further diagnostic tests
- is considered by the investigator to be of clinical significance

### Serious Adverse Event

Adverse events are classified as serious or non-serious. A **serious adverse event** is any AE that is:

- fatal
- life-threatening
- requires or prolongs hospital stay
- results in persistent or significant disability or incapacity
- a congenital anomaly or birth defect
- an important medical event

Important medical events are those that may not be immediately life threatening, but are clearly of major clinical significance. They may jeopardize the subject, and may require intervention to prevent one of the other serious outcomes noted above. For example, drug overdose or abuse, a seizure that did not result in in-patient hospitalization, or intensive treatment of bronchospasm in an emergency department would typically be considered serious.

All adverse events that do not meet any of the criteria for serious should be regarded as **non-serious adverse events**.

### **Adverse Event Reporting Period**

The study period during which adverse events must be reported is normally defined as the period from the initiation of any study procedures to the end of the study treatment follow-up. For this study, the study treatment follow-up is defined as 30 days following the last administration of study treatment.

### **Preexisting Condition**

A preexisting condition is one that is present at the start of the study. A preexisting condition should be recorded as an adverse event if the frequency, intensity, or the character of the condition worsens during the study period.

### **General Physical Examination Findings**

At screening, any clinically significant abnormality should be recorded as a preexisting condition. At the end of the study, any new clinically significant findings/abnormalities that meet the definition of an adverse event must also be recorded and documented as an adverse event.

### **Post-study Adverse Event**

All unresolved adverse events should be followed by the investigator until the events are resolved, the subject is lost to follow-up, or the adverse event is otherwise explained. At the last scheduled visit, the investigator should instruct each subject to report any subsequent event(s) that the subject, or the subject's personal physician, believes might reasonably be related to participation in this study. The investigator should notify the study sponsor of any death or adverse event occurring at any time after a subject has discontinued or terminated study participation that may reasonably be related to this study. The sponsor should also be notified if the investigator should become aware of the development of cancer or of a congenital anomaly in a subsequently conceived offspring of a subject that has participated in this study.

### **Abnormal Laboratory Values**

A clinical laboratory abnormality should be documented as an adverse event if any one of the following conditions is met:

- The laboratory abnormality is not otherwise refuted by a repeat test to confirm the abnormality
- The abnormality suggests a disease and/or organ toxicity
- The abnormality is of a degree that requires active management; e.g. change of dose, discontinuation of the drug, more frequent follow-up assessments, further diagnostic investigation, etc.

### **Hospitalization, Prolonged Hospitalization or Surgery**

Any adverse event that results in hospitalization or prolonged hospitalization should be documented and reported as a serious adverse event unless specifically instructed otherwise in this protocol. Any condition responsible for surgery should be documented as an adverse event if the condition meets the criteria for an adverse event.

Neither the condition, hospitalization, prolonged hospitalization, nor surgery are reported as an adverse event in the following circumstances:

- Hospitalization or prolonged hospitalization for diagnostic or elective surgical procedures for a preexisting condition. Surgery should **not** be reported as an outcome of an adverse event if the purpose of the surgery was elective or diagnostic and the outcome was uneventful.
- Hospitalization or prolonged hospitalization required to allow efficacy measurement for the study.
- Hospitalization or prolonged hospitalization for therapy of the target disease of the study, unless it is a worsening or increase in frequency of hospital admissions as judged by the clinical investigator.

## **8.2 Recording of Adverse Events**

At each contact with the subject, the investigator must seek information on adverse events by specific questioning and, as appropriate, by examination. Information on all adverse events should be recorded immediately in the source document, and also in the appropriate adverse event module of the case report form (CRF). All clearly

related signs, symptoms, and abnormal diagnostic procedures results should be recorded in the source document, though they should be grouped under one diagnosis.

All adverse events occurring during the study period must be recorded. The clinical course of each event should be followed until resolution, stabilization, or until it has been determined that the study treatment or participation is not the cause. Serious adverse events that are still ongoing at the end of the study period must be followed up to determine the final outcome. Any serious adverse event that occurs after the study period and is considered to be possibly related to the study treatment or study participation should be recorded and reported immediately.

### **8.3 Reporting of Serious Adverse Events and Unanticipated Problems**

Investigators must conform to the adverse event reporting timelines, formats and requirements of the various entities to which they are responsible. At a minimum, serious adverse events (SAEs) that must be reported to the principal investigator (PI), or the covering BMT Attending on the Transplant Service, are those that are:

- related to study participation,
- unexpected, and
- serious or involve risks to subjects or others  
(see definitions, section 8.1).

If the report is supplied as a narrative, the minimum necessary information to be provided at the time of the initial report includes:

- Study identifier
- Study Center  
(if multi-center study)
- Subject number
- A description of the event
- Date of onset
- Current status
- Whether study treatment was discontinued
- The reason why the event is classified as serious
- Investigator assessment of the association between the event and study treatment

### **8.3.1 Investigator reporting: notifying the PI**

Any study-related unanticipated problem posing risk of harm to subjects or others, and any type of serious adverse event, must be reported to the PI by telephone within 24 hours of the event. To report such events, a Serious Adverse Event (SAE) form must be completed by the investigator and faxed to the study sponsor within 24 hours. The investigator will keep a copy of this SAE form on file at the study site. Report serious adverse events by phone and facsimile to:

[name]  
Section of Hematology/Oncology  
Norris Cotton Cancer Center  
Dartmouth-Hitchcock Medical Center  
[name]  
[name]  
[contact]

Within the following 48 hours, the investigator must provide further information on the serious adverse event or the unanticipated problem in the form of a written narrative. This should include a copy of the completed Serious Adverse Event form, and any other diagnostic information that will assist the understanding of the event. Significant new information on ongoing serious adverse events should be provided promptly to the study sponsor

### **8.3.2 Investigator reporting: notifying the Dartmouth IRB**

This section describes the requirements for safety reporting by investigators who are Dartmouth faculty, affiliated with a Dartmouth research site, or otherwise responsible for safety reporting to the Dartmouth IRB. The Dartmouth College IRB (CPHS) requires expedited reporting of those events related to study participation that are unforeseen and indicate that participants or others are at increased risk of harm. The Dartmouth IRB will not acknowledge safety reports or bulk adverse event submissions that do not meet the criteria outlined below. The Dartmouth IRB requires researchers to submit reports of the following problems, once the investigator becomes aware of the event:

1. Unanticipated problems that are serious adverse events should be reported to the IRB within 1 week of the investigator becoming aware of the event.
2. Any other unanticipated problem should be reported to the IRB within 2 weeks of the investigator becoming aware of the problem.

Unanticipated Problem Involving Risks to Subjects or Others (UPRs) Any incident, experience or outcome that meets ALL 3 of the following criteria:

1. Is unexpected (in terms of nature, specificity, severity, or frequency) given (a) the research procedures described in the protocol-related documents, such as the IRB-approved protocol and informed consent document and (b) the characteristics of the subject population being studied; AND
2. Is related or possibly related to participation in the research (possibly related means there is a reasonable possibility that the incident, experience, or outcome may have been caused by the procedures involved in the research); AND
3. Suggests that the research places subjects or others at greater risk of harm (including physical, psychological, economic, legal, or social harm) than was previously known or recognized.

Unanticipated Problems Involving Risks to Subjects or Others (UPRs) may be medical or non-medical in nature, and include – but are not limited to – serious, unexpected, and related adverse events and unanticipated adverse device effects (see below). Please note that adverse events (as defined below) are reportable to the IRB as UPRs only if they meet all 3 criteria listed above.

#### **Reporting Process**

Unanticipated problems posing risks to subjects or others as noted above will be reported to the Dartmouth IRB via the RAPPORT format, using the form: “Unanticipated Problems Posing Risks to Subjects or Others Including Reportable Adverse Events” or as a written report of the event (including a description of the event with

information regarding its fulfillment of the above criteria, follow-up/resolution and need for revision to consent form and/or other study documentation).

Copies of each report and documentation of IRB notification and receipt will be kept in the Clinical Investigator's study file.

### **Other Reportable events:**

For clinical drug trials, the following events are also reportable to the Dartmouth IRB:

- Any adverse experience that, even without detailed analysis, represents a serious unexpected adverse event that is rare in the absence of drug exposure (such as agranulocytosis, hepatic necrosis, Stevens-Johnson syndrome).
- Any adverse event that would cause the PI to modify the protocol or informed consent form, or would prompt other action by the IRB to assure protection of human subjects Information that indicates a change to the risks or potential benefits of the research, in terms of severity or frequency. For example:
  - An interim analysis indicates that participants have a lower rate of response to treatment than initially expected.
  - Safety monitoring indicates that a particular side effect is more severe, or more frequent than initially expected
  - A paper is published from another study that shows that an arm of your research study is of no therapeutic value.
- Change in FDA safety labeling or withdrawal from marketing of a drug, device, or biologic used in a research protocol.
- Breach of confidentiality
- Change to the protocol taken without prior IRB review to eliminate apparent immediate hazard to a research participant.
- Incarceration of a participant when the research was not previously approved under Subpart C and the investigator believes it is in the best interest of the subject to remain on the study.
- Complaint of a participant when the complaint indicates unexpected risks or the complaint cannot be resolved by the research team.
- Protocol violation (meaning an accidental or unintentional deviation from the IRB approved protocol) that in the opinion of the investigator placed one or more participants at increased risk, or affects the rights or welfare of subjects.

### **8.3.3 Investigator reporting: Notifying a another IRB**

N/A

### **8.3.4 Sponsor reporting: Notifying the FDA**

- **Within 7 calendar days**  
Any study event that is:
  - associated with the use of the study drug
  - unexpected,
  - fatal or life-threatening, and
- **Within 15 calendar days**  
Any study event that is:
  - associated with the use of the study drug,
  - unexpected, and
  - serious, but not fatal or life-threatening

-or-

  - a previous adverse event that was not initially deemed reportable but is later found to fit the criteria for reporting (reporting within 15 calendar days from when event was deemed reportable).

Any finding from tests in laboratory animals that:

  - suggests a significant risk for human subjects including reports of mutagenicity, teratogenicity, or carcinogenicity.

## Reporting Process

Adverse events may be submitted on FDA Form 3500A or in a narrative format. If supplied as in a narrative format, the minimum information to be supplied is noted above at the beginning of section 8.3.

## 8.4 Unblinding Procedures

N/A

## 8.5 Stopping Rules

Within-Subject Dose-Escalation Study stopping rules-

### Initial cohort (first 5 patients accrued) will be treated as follows:

Ibrutinib 140 mg po once daily with

Rituximab 375 mg/m^2 IV weekly x4 (with pre-medications and infusion procedure as per standard protocol)

Rituximab Pre-medications: Acetaminophen 650 mg po; Diphenhydramine 25 mg po/IV; Dexamethasone 20 mg IV

If no adverse events  $\geq$  nonhematologic grade 3 or  $\geq$  hematologic grade 4 are noted after 1 week at 140 mg daily, the Ibrutinib dose schedule will be increased to 280 mg daily

If no adverse events  $\geq$  nonhematologic grade 3 or  $\geq$  hematologic grade 4 are noted after 1 week at 280 mg daily, the Ibrutinib dose schedule will be increased to 420 mg daily.

If grade  $\geq$  3 non-hematologic toxicity and/or grade 4 hematologic toxicity are noted, a dose de-escalation to the prior dose level will be made. Resumption of treatment at this dose level may begin once Ibrutinib toxicity has improved to the grade 1 (or baseline) level.

If a  $\geq$  nonhematologic grade 3 or  $\geq$  hematologic grade 4 adverse event is noted in any one of the 5 subjects at the 140 mg dose level, a thorough review of this AE will be undertaken, and if deemed causative, treatment for that subject will be discontinued.

If a  $\geq$  nonhematologic grade 3 or  $\geq$  hematologic grade 4 adverse event is noted in  $>2$  of the 5 subjects at the 140 mg dose level, the study will be discontinued.

If a  $\geq$  nonhematologic grade 3 or  $\geq$  hematologic grade 4 adverse event is noted in a subject at the 280 mg dose level, the subject will then be dropped back to the prior dose level or treatment for that subject will be discontinued.

If a  $\geq$  nonhematologic grade 3 or  $\geq$  hematologic grade 4 adverse event is noted in a subject at the 420 mg dose level, the subject will then be dropped back to the prior dose level or treatment for that subject will be discontinued.

If therapy for 2 or more subjects at either the 280 mg or 420 mg dose level requires discontinuation, per the above parameters, no further escalation to those dose levels will be attempted for future patients.

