## Study Summary

Title	Combination Ibrutinib and Rituximab for Treatment of Chronic Graft-Versus-Host Disease Following Allogeneic Stem Cell Transplant
Short Title	Ibrutinib and Rituximab for Steroid-Refractory or Dependent Chronic GVHD
Protocol Number	D17120
Phase	Phase 1/2
Methodology	Open label, Within-Subject Dose-Escalation Study
Study Duration	2 years (patients will be followed after 6 months for survival only)
Study Center(s)	Single center
Objectives	To determine the safety and efficacy of Ibrutinib and Rituximab combination therapy for steroid-refractory or -dependent chronic GVHD following allogeneic stem cell transplant.
Number of Subjects	15
Diagnosis and Main Inclusion Criteria	Steroid refractory or dependent chronic graft-versus-host disease (diagnosis to be based on histologic sampling and/or via clinical criteria; see Attachments) > 18 years old Karnofsky Performance Status 60 or greater

Study Product, Dose, Route, Regimen	
Within-Subject Dose-Escalation Format:
 
 
-The first 5 subjects will receive treatment as follows: 
 
-Ibrutinib 140 mg po once daily
 
-Rituximab 375 mg/m^2 IV weekly x4
 
 
 
-Adverse events will be defined as per the NCI Common Terminology Criteria for Adverse Events (CTCAE) 
 
-if no adverse events <math>\geq</math> non-hematologic grade 3 or <math>\geq</math> hematologic grade 4 are noted after 1 week at 140 mg daily, the Ibrutinib dose schedule will be increased to 280 mg daily
 
-if no adverse events <math>\geq</math> non-hematologic grade 3 or <math>\geq</math> to hematologic grade 4 are noted after 1 week at 280 mg daily, the Ibrutinib dose schedule will be increased to 420 mg daily
 
- the potential exists for a 2nd weekly x4 Rituximab course 8 weeks after initial Rituximab therapy, if no response or an incomplete response is noted
 
 
 
 
Expansion cohort:
 
 
- following accrual of the 5 initial subjects, an additional 10 subjects will be accrued, with dosing to be informed by the results of the within-subject dose escalation cohort
 

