### 5.1.1 Details of the Treatment Regimen

**Initial cohort (first 5 patients accrued) will be treated as follows:**

Ibrutinib 140 mg po once daily with

Rituximab 375 mg/m^2 IV weekly x4 (with pre-medications and infusion procedure as per standard protocol)

Rituximab Pre-medications: Acetaminophen 650 mg po; Diphenhydramine 25 mg po/IV; Dexamethasone 20 mg IV

If no adverse events  $\geq$  nonhematologic grade 3 or  $\geq$  hematologic grade 4 are noted after 1 week at 140 mg daily, the Ibrutinib dose schedule will be increased to 280 mg daily

If no adverse events  $\geq$  nonhematologic grade 3 or  $\geq$  hematologic grade 4 are noted after 1 week at 280 mg daily, the Ibrutinib dose schedule will be increased to 420 mg daily.

If grade  $\geq$  3 non-hematologic toxicity and/or grade 4 hematologic toxicity are noted, a dose de-escalation to the prior dose level will be made. Resumption of treatment at this dose level may begin once Ibrutinib toxicity has improved to the grade 1 (or baseline) level.

If a  $\geq$  nonhematologic grade 3 or  $\geq$  hematologic grade 4 adverse event is noted in any one of the 5 subjects at the 140 mg dose level, a thorough review of this AE will be undertaken, and if deemed causative, treatment for that subject will be discontinued.

If a  $\geq$  nonhematologic grade 3 or  $\geq$  hematologic grade 4 adverse event is noted in  $>2$  of the 5 subjects at the 140 mg dose level, the study will be discontinued.

If a  $\geq$  nonhematologic grade 3 or  $\geq$  hematologic grade 4 adverse event is noted in a subject at the 280 mg dose level, the subject will then be dropped back to the prior dose level or treatment for that subject will be discontinued.

If a  $\geq$  nonhematologic grade 3 or  $\geq$  hematologic grade 4 adverse event is noted in a subject at the 420 mg dose level, the subject will then be dropped back to the prior dose level or treatment for that subject will be discontinued.

If therapy for 2 or more subjects at either the 280 mg or 420 mg dose level requires discontinuation, per the above parameters, no further escalation to those dose levels will be attempted for future patients.

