### Expansion cohort (additional 10 patients accrued) will be treated as follows:

Ibrutinib 420 mg po once daily with

Rituximab 375 mg/m^2 IV weekly x4

If, based on above toxicity criteria, the Ibrutinib 420 mg daily dose schedule has been discontinued, then 280 mg po once daily will be the expansion cohort dose schedule

If, based on above toxicity criteria, the Ibrutinib 280 mg daily dose schedule has been discontinued, then 140 mg po once daily will be the expansion cohort dose schedule

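### The stopping rules count a treatment-related death like a survivable grade 3/4 event: in the first 5 subjects, one at 280 or 420 mg, with no other discontinuation at that level, requires no hold, stop or dose change for anyone else

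*Combined protocol and SAP*

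**What the plan says.** Section 8.5 repeats the dosing rules of 5.1.1 for the first 5 subjects. Every rule is keyed to the same class of event: nonhematologic grade 3 or above, or hematologic grade 4 or above.

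- **140 mg, one subject with an event:** "a thorough review of this AE will be undertaken, and if deemed causative, treatment for that subject will be discontinued".
- **140 mg, study stop:** if events occur in more than 2 "of the 5 subjects at the 140 mg dose level, the study will be discontinued".
- **280 or 420 mg, one subject with an event:** "the subject will then be dropped back to the prior dose level or treatment for that subject will be discontinued".
- **280 or 420 mg, cohort rule:** "If therapy for 2 or more subjects at either the 280 mg or 420 mg dose level requires discontinuation", then "no further escalation to those dose levels will be attempted for future patients".
- **Expansion cohort:** 10 further subjects start at 420 mg. The dose drops to 280 mg on this condition: "If, based on above toxicity criteria, the Ibrutinib 420 mg daily dose schedule has been discontinued". The Study Summary puts it more loosely, "with dosing to be informed by the results of the within-subject dose escalation cohort".

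Death is named in the definition of a serious adverse event (8.1) and in the FDA reporting timelines (8.3.4). It is not named in 5.1.1 or 8.5.

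**The concern.** Safety is the only primary endpoint (3.2). Section 1.5 gives the reason for escalating within subjects: the combination was tolerated in patients with chronic lymphocytic leukemia, but they had not had an allogeneic transplant. The escalation rules are therefore the trial's main protection against an unexpected hazard in this population.

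Those rules seem to have been written with survivable events in mind. Stepping back one dose level, and resuming once toxicity has settled, cannot apply to a subject who has died. If a death is simply counted as one more qualifying event, a site could follow 8.5 to the letter, keep enrolling and keep escalating, with no study-level decision required first.

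**Working it through.** The stopping rules state thresholds but no operating characteristics, so there is no figure of the plan's to reproduce. The power figures in 7.1 concern response rates and have no bearing here. The check is a count of each scenario against its threshold, followed by a look at what else the protocol requires.

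**Step 1. Does a death fall in the event class?** Yes. Both thresholds are open at the top, so a fatal event qualifies. It carries no extra weight.

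**Step 2. Count against threshold, first 5 subjects.** The escalation criteria are read subject by subject, as the within-subject format in 3.1 implies.

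| Scenario | Count | Threshold | Met? | Required for other subjects |
|---|---|---|---|---|
| One related death at 280 or 420 mg, no other discontinuation at that level | 1 discontinuation | at least 2 | No (1 < 2) | Nothing |
| Two related deaths at 140 mg, no other qualifying event | 2 of 5 | more than 2, so at least 3 | No (2 < 3) | Nothing |

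Three details of the first row:

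- Counting the death as a discontinuation is the generous reading. If it were not counted, the tally would be 0.
- The rule does not say whether 280 and 420 mg discontinuations are pooled. If they are, the condition becomes no other discontinuation at either level.
- The rule counts discontinuations, not events. Another subject who has a qualifying event and is stepped back does not bring the count to 2.

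**Step 3. Expansion dose.** It moves off 420 mg only if the same criteria have discontinued that dose. In neither row have they done so, so 420 mg stands.

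**Step 4. How many subjects are affected?** At most (5 − 1) + 10 = 14 others, if the death is in the first subject before anyone else starts.

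**Step 5. What else applies after a related death?**

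| Provision | What it does | Requires a pause? |
|---|---|---|
| 8.3.1 | Telephone report to the principal investigator within 24 hours | No |
| 8.3.2 | IRB report within 1 week if an unanticipated problem; also reportable if the event would lead to a protocol change or IRB action | No |
| 8.3.4 | FDA report within 7 days if drug-associated, unexpected and fatal | No |
| 8.5, 140 mg review | Decides treatment for the affected subject only | No |
| 10.1 | Regular assessment of serious events | No |
| 4.4.1 | Any protocol physician may stop the study; no criterion given | No |
| 10.2 | The Data Safety Monitoring and Accrual Committee (DSMAC) may suspend; no event triggers a review | No |
| Study Summary | Expansion dosing takes account of the first cohort | No |
| Monitoring plans named in 10.1 and 10.3 | Not reproduced | Unknown |

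Every visible provision reports an event or permits action. None requires a decision before the next enrolment or dose increase.

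**The case against.** The strongest reply is that a 15-subject, single-center, open-label study can leave the response to one death to judgment. The principal investigator hears within 24 hours and oversees site safety. The documents give no accrual rate, but if 15 subjects started evenly over 18 to 24 months (an assumption), one would start every 78/15 = 5.2 to 104/15 = 6.9 weeks on average. The 24-hour report, and the 1-week and 7-day reports where they apply, would come before an average next start, and few subjects would be mid-escalation at the time. In addition, 1.5 describes ibrutinib 420 mg as safe and effective in post-transplant disease and says the rituximab schedule has been used in several prospective studies, so only the combination in transplant recipients is new.

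This stands as far as practical risk goes: someone with authority would probably act. It does not supply a required action, and a stopping-rules section exists so that the response to the gravest outcome does not depend on discretion.

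A second reply is that the monitoring plans named in 10.1 and 10.3 may contain a death trigger. That cannot be excluded. The point is therefore limited to what 8.5 contains or cites, which includes no such trigger.

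A third is that the remedy reaches beyond the first 5 subjects. It does, deliberately. The cohort rule speaks of future patients but sits under the initial-cohort heading and refers to escalation, so its reach into the expansion cohort is unclear. Wording that applies to both cohorts removes the doubt.

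**Conclusion.** The point holds and should be acted on. Sections 5.1.1 and 8.5 do not distinguish a related death from a survivable qualifying event. One such death at 280 or 420 mg in the first 5 subjects, with no other discontinuation at that level, leaves every prespecified rule for other subjects unchanged and keeps 420 mg as the expansion dose. This follows from counting and rests on no assumed rate.

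Three stronger readings are tempting and are not supported:

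- **That the 140 mg rule is an equal hazard.** Two related deaths there do fall short of the stop, but the case is remote. An event-free subject spends only 1 week at that dose, and the stop rule counts qualifying events whether or not they are related, so one event in a third subject would trigger it.
- **That a death could wait a full quarter for review.** Section 10.2 says the committee meets quarterly, but leaves the frequency of its review to the Clinical Cancer Review Committee (CCRC). The interval for this study is not stated.
- **That the gap has a known probability, or that a death would go unaddressed.** The documents give no related-death or discontinuation rate, and figures from invented rates would only restate that 1 is below 2 and 2 is below 3. Reporting and discretionary powers exist; what is missing is a required pause.

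**What to change.** Add one sentence to both 5.1.1 and 8.5: after any death judged at least possibly related to ibrutinib or rituximab, in either cohort and at any dose, new enrolment and dose escalation pause until an ad hoc DSMAC review decides whether, and at what dose, the study continues. Agree the ad hoc review with the CCRC in advance. If the monitoring plan named in 10.1 or 10.3 already has such a trigger, cite it in 8.5 instead.

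This uses an existing committee and changes neither sample size nor analysis. The cost is a short accrual pause after each such death. Under the assumed accrual above, a 4-week pause would delay 4/6.9 = 0.6 to 4/5.2 = 0.8 of a start. In an immunosuppressed population the possibly-related threshold may catch more than one death, but each brings a review, not an automatic stop. If no ad hoc meeting could be arranged, the pause could run to the committee's next scheduled meeting, which is the reason to settle the arrangement beforehand.
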